7.4. Per Protocol Set (PPS), Immunogenicity Set

PPS-1: Booster immunogenicity analysis:

All subjects in the FAS-1 Immunogenicity who:

- Have no major PD leading to exclusion (see section [6.2](#))
- Are not excluded due to other reasons such as withdrawal of consent (see section [6.2](#))

PPS-2: Long term immunogenicity analysis:

All subjects in the FAS-2 Immunogenicity who:

- Have no major PD leading to exclusion (see section [6.2](#))

- Are not excluded due to other reasons such as withdrawal of consent (see section 6.2)

Immunogenicity analyses will be repeated on PPS if it differs from FAS for more than 10% (by objective).

7.5. Safety Set

Safety Set

All subjects who are exposed to booster dose and report safety data.

7.5.1. Restricted Safety Set

Not applicable

7.6. Other Analysis Set

None

7.7. Overview of Analysis Sets by PD Code

Table 4 Safety Sets: applicable to Exposed to Booster dose subjects only

PD code	PD Description and Exclusion Reasons	Study Objective/Period	Exposed Set	Safety Set	
			Exclusion code	EXPFL	SAFFL
1070	incomplete treatment course. Booster was not administered although subject had RVNA concentration of <0.5 IU/mL	All Study		EXC	EXC
2150	Subject did not provide any post-booster safety data	Approx. 6 months after booster exposure*			EXC

* For further details refer to study protocol

EXC = excluded from this analysis set.

Table 5 Immunogenicity Sets

PD code	PD Description and Exclusion Reasons	All ENROLLED	FAS 1	FAS 2	PPS 1	PPS 2
		Exclusion code	ENRFL	FAS10FL	FAS20FL	PPS10FL
800	Fraudulent data		EXC	EXC	EXC	EXC
900	Signed informed consent not available on site				EXC	EXC
900	Wrong informed consent version signed				EXC	EXC
900	Informed consent not signed and/or dated by subject				EXC	EXC
900	Informed consent not signed and/or dated by appropriate site staff.				EXC	EXC
900	Informed consent not signed prior to any study procedure (examples: a, b, c)				EXC	EXC
900	Other informed consent deviations				EXC	EXC
910	Partially or inappropriately signed ICF				EXC	EXC
1070	Booster was administered although subject had RVNA concentration ≥ 0.5 IU/mL			EXC	EXC	EXC
1070	Route of administration is wrong or unknown				EXC	
1070	Administration of booster vaccine at wrong visit				EXC	
1070	Commercial vaccine used in place of study vaccine (but same vaccine)				EXC	
1070	Study treatment administered while contraindication				EXC	
1070	Study treatment not prepared as per protocol (e.g. reconstitution)				EXC	
1070	Incorrect Volume was given				EXC	
1080	Use of study treatment impacted by a temperature excursion which was not reported or approved, or which was disapproved for further use.				EXC	
1090	Expired study treatment administered				EXC	
2010	Eligibility Criteria Not Met				EXC	EXC
2040	Prohibited concomitant medication (interval + type)				EXC	EXC
2040	Prohibited concomitant vaccination (interval + type)				EXC	EXC

PD code	PD Description and Exclusion Reasons	All ENROLLED	FAS 1	FAS 2	PPS 1	PPS 2
		ENRFL	FAS10FL	FAS20FL	PPS10FL	PPS20FL
2040	Other excluded medication, vaccine or device deviation				EXC	EXC
2090	Blood draw after booster dose outside 7 (+/- 1 day) day interval				EXC	EXC
2090	Did not comply with blood draw schedule (for annual Scheduled Clinic Visits): yearly blood draw outside +/- 42 days interval				EXC	EXC
2100	PII recorded in label of sample		EXC	EXC	EXC	EXC
2100	Low volume (not sufficient to perform testing)		EXC	EXC	EXC	EXC
2100	No samples collected for subject (and should have been collected)		EXC	EXC	EXC	EXC
2100	Mislabelling (sample not tested)		EXC	EXC	EXC	EXC
2100	Serological results not available		EXC	EXC	EXC	EXC
2120	Assessment not properly performed				EXC	EXC
2120	Temperature deviation from range defined in protocol and/or SPM/lab manual - -- 18 to -12C Freezer				EXC	EXC
2120	Incorrect spinning/processing of sample				EXC	EXC
2120	Central/internal/external lab deviations				EXC	EXC
2120	Mislabelling (sample tested)				EXC	EXC
2130	Testing performed on samples not aligned with ICF				EXC	EXC

FAS = Full Analysis Set; PPS=Per Protocol Set; EXC = excluded from this analysis set.

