3. STUDY DESIGN

This is a phase 3, open-label, non-randomized multicenter, extension study in healthy adults. In the parent study (V49_23) subjects from ≥ 18 years to ≤ 65 years of age were randomized to one of four vaccination groups, three of which for rabies pre-exposure prophylaxis according to conventional (1.0 mL dose of PCEC rabies vaccine administered IM on each of days 1, 8 and 29) regimen, alone or in combination with Japanese Encephalitis (JE) vaccination according to the study group (see [Table 1](#) below) or to a new, one-week, accelerated (1.0 mL dose of PCEC rabies vaccine administered IM on each of days 1, 4 and 8) regimen in combination with JE vaccination.

Table 1 Vaccine Groups in Studies V49_23 and V49_23E1

V49_23 study			V49_23E1 study	
Arm Code (Arm)	Study Vaccine Group N of subjects who received full PrEP and completed the study	Regimen of Primary Vaccine Administration	Study Vaccine Group (from V49_23) Maximum N of subjects who will be invited for enrollment	Regimen of Booster Vaccination
A (Conv-R/JE)	Conventional Rabies + JE vaccination N=158 subjects	Rabies PrEP Days 1, 8 and 29 JE primary series Days 1 and 29	Conv-R/JE N= up to 158 subjects	A single PCEC rabies booster dose (1.0 mL) IM for subjects with RVNA concentrations <0.5IU/mL
B (Acc-R/JE)	Accelerated Rabies + JE vaccination N=209 subjects	Rabies PrEP Days 1, 4 and 8 JE primary series Days 1 and 8	Acc-R/JE N= up to 209 subjects	A single PCEC rabies booster dose (1.0 mL) IM for subjects with RVNA concentrations <0.5IU/mL
C (Conv-R)	Conventional Rabies N=211 subjects	Rabies PrEP Days 1, 8 and 29	Conv-R N= up to 211 subjects	A single PCEC rabies booster dose (1.0 mL) IM for subjects with RVNA concentrations <0.5IU/mL
D (Conv-JE)	Conventional JE N=52 subjects	JE primary series Days 1 and 29	NA	NA

Source: Table 3.1-1 of Protocol Amendment 2 (25 FEB 19)

Subjects who were randomized into one of the 3 rabies vaccination groups (arms A, B and C) of the parent study V49_23, who received the full PrEP rabies regimen and completed V49_23 study following study protocol will be invited to take part to this study.

Subjects who were randomized to the JE conventional group (arm D) in the parent study V49_23 will not be invited to take part to this extension study.

Subjects will receive their booster doses based on their individual antibody concentrations measured over time, i.e., booster will be administered only to those subjects with RVNA concentrations <0.5 IU/mL.

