- ^a Ad hoc Clinic Visit (which is planned to occur as soon as the results of the antibody assay will be available and within approximately 6 months from the blood draw taken during a previous "Scheduled Clinic Visit") is only applicable for those subjects with RVNA concentrations <0.5 IU/mL during this extension study. See sections 3.1 and 3.9 of Protocol Amendment 2 for further details.
- ^b Additional Clinic Visit (within approximately 7 days from Ad hoc Clinic Visit) only applicable for subjects who will receive a booster dose of PCEC rabies vaccine during Ad hoc Clinic Visit.
- ^c Procedure to be performed prior to vaccination. Physical exams have to be done by practitioners in accordance with their institutional policy. Should the physical assessment reveal any abnormal values or events, which fall under definition of SAE, these must be documented in the CRF Adverse Events Form and reported to sponsor.
- ^d Only for female subject of childbearing potential who are eligible to receive the booster dose.
- ^e GSK Biologicals' Randomization System on Internet (SBIR) will be used for Treatment allocation.
- ^f SAEs and the associated concomitant medications will be collected starting from the booster administration and until the completion of safety follow-up period (the day of the next Scheduled Clinic Visit after booster vaccination or on the date of Early Termination Visit, whichever is earlier).

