8.8. Derived and Computed Variables

Data from parent study (V49_23)

Time to event analysis

For time to event analysis (i.e., Kaplan-Meier (KM) and Cox proportional hazard regression model), immunogenicity data from parent study, from day 57 up to one year, as well as data related to time between the end of parent study and start of this study (i.e., if subject receives a booster between the two studies) will be considered, as estimation of time to RVNA concentration drop below 0.5IU/mL.

Long term immunogenicity analysis

Demographics

Race and Age at time of V49_23 enrolment will be derived from demography of the parent study.

Body Mass Index (kg/m²) (BMI) will be calculated using the following formula: Weight (kg) / Height² (m²)

Time to Event

Survtime represents time to event/censoring in years:

Survtime variable will be derived using the planned visit day at which the event occurred or the subject is censored as time point.

The following SAS code describes how to derive **Survtime** from V49_23 study and from the current study (V49_23E1).

```

DATA <dbname>;
  SET <dbname>;
  IF LBORRES IN ('<0.1', '0.1', '0.2', '0.3', '0.4')
  THEN DROP ='Y';
  ELSE DROP ='N';
  format LABEL $12.;
  IF STUDYID = 'V49_23' THEN DO;
    IF VISITNUM = 9 THEN do;POINT =1; YEAR =57; LABEL = 'Day 57'; end;
    IF VISITNUM = 10 THEN do;POINT =2; YEAR =91; LABEL = 'Day 91'; end;
    IF VISITNUM = 11 THEN do;POINT =3; YEAR =181; LABEL = 'Day
181';end;
    IF VISITNUM = 12 THEN do;POINT =4; YEAR =365;LABEL = 'Day 366';end;
  END;
  IF STUDYID = 'V49_23E1' THEN DO;
    IF VISITNUM = 1 THEN do; YEAR = 3*365; LABEL = 'Year 3'; end;
    IF VISITNUM = 2 THEN do; YEAR = 4*365; LABEL = 'Year 4'; end;
    IF VISITNUM = 3 THEN do; YEAR = 5*365; LABEL = 'Year 5'; end;
    IF VISITNUM = 4 THEN do; YEAR = 6*365; LABEL = 'Year 6'; end;
    IF VISITNUM = 5 THEN do; YEAR = 7*365; LABEL = 'Year 7'; end;
    IF VISITNUM = 6 THEN do; YEAR = 8*365; LABEL = 'Year 8'; end;
    IF VISITNUM = 7 THEN do; YEAR = 9*365; LABEL = 'Year 9'; end;
    IF VISITNUM = 8 THEN do; YEAR = 10*365; LABEL = 'Year 10';end;
  END;
  Survtime= YEAR;

  IF DROP ='Y' THEN CENSOR=1; ELSE CENSOR = 0;
RUN;

```

Censor: represents censoring indicator variable: 0=censored, 1=event of interest;

Event of interest: RVNA concentration < 0.5 (censor=1)

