All further subject immunogenicity data will not be used for Time to event analysis.

GMC and percentage analysis - boostability:

Subject is included in the Exposed to Booster Set and independently on time or visit in which booster is administered the time-points will be as following:

- Pre-booster
- 7 days after booster
- 6 to 9 months after booster

Long-term persistence of antibody responses after primary series

All immunogenicity data until booster will be part of analysis as they are reported.

For subjects receiving a booster dose, the following method of imputation will be used for antibody values:

- Values, missing or not, will be replaced with half of the quantification level (0.1 IU/mL) from that moment onward.

Subjects receiving a booster dose outside of the study and for which RVNA value at the time of booster vaccination is not available will be excluded from FAS-2 and PPS-2 (see section 7.3 for details)

Duration in the Study

Duration in the study is defined in days as:

Last visit date (visit x)^a – Enrollment date (visit 1) + 1

^a or premature discontinuation date (in case of withdrawal from the study)

The duration is missing if one of the dates is missing or incomplete.

Unsolicited Serious Adverse Events

All serious adverse events (AEs) following *Rabipur* booster dose within the study will be characterized according to the date of occurrence related to the vaccination phase as follows:

- **Emergence before vaccination phase:** start date before the first date of injection of study vaccine.
- **Emergence during vaccination phase:** start date on or after the first date of injection of study vaccine or, adverse event increase in severity including to “serious” AE.

If start date is equal to the first date of injection then “timing” variable (“On injection day, before injection”/“On injection day, after injection”) will be used to define whether the adverse event occur before or after the injection.

If an AE start date is missing or unknown, the AE will be considered as emergent.

When start and/or end dates of an AE are only partially known, AEs will be categorized as emergent before, during, or after vaccination phase using the following rules:

- If the partial end date is before ($<$) the first study vaccination (i.e., year or year & month is/are before the first study vaccination year or year & month) then the AE is emergent before vaccination phase.

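### SAP Table 5 excludes subjects from the long-term persistence set PPS-2 for a mistimed 7-day post-booster draw, and that row can remove only subjects who already have the persistence event

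*SAP*

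**What the plan says.** SAP Section 7.7, Table 5, lists deviations by code and marks with EXC each analysis set from which the subject is removed. Under code 2090, the row "Blood draw after booster dose outside 7 (+/- 1 day) day interval" is EXC for PPS-1 and PPS-2 and blank for FAS-1 and FAS-2.

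Other booster deviations are treated differently. The row "Route of administration is wrong or unknown" is EXC for PPS-1 only. So are seven more rows: wrong visit, commercial vaccine, contraindication, preparation, volume, temperature excursion and expired vaccine. The row "Booster was administered although subject had RVNA concentration ≥ 0.5 IU/mL" already excludes at FAS-2.

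The footnotes to SAP Table 3 say that the visit for the 7-day draw is "only applicable for subjects who will receive a booster dose of PCEC rabies vaccine during Ad hoc Clinic Visit". SAP Section 3 adds that "booster will be administered only to those subjects with RVNA concentrations <0.5 IU/mL". Section 8.8 defines the time-to-event outcome as RVNA below 0.5 IU/mL and does not use a subject's later data in that analysis. For long-term persistence, "All immunogenicity data until booster will be part of analysis as they are reported"; from then on values are replaced by 0.1 IU/mL.

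SAP Section 7.4 builds PPS-2 from FAS-2 subjects with no exclusionary major deviation. Immunogenicity analyses are repeated on the PPS only when it differs from the FAS by more than 10%, judged by objective. Protocol Section 8.3.5 also defines the PPS by objective and applies correct booster receipt to boostability only.

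**The concern.** A per-protocol set for persistence should drop subjects whose deviation could distort their persistence data. The timing of a blood draw taken after the event and after the booster cannot do that. What the deviation does require is that the subject was boosted, which in FAS-2 means that RVNA had already fallen below 0.5 IU/mL. A subject who stays above the threshold for ten years can never be removed by this row.

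The first primary objective compares regimens on the time to that fall. If PPS-2 is run as a check on FAS-2, it carries an exclusion that depends on the outcome and always pushes persistence upward. The yearly GMCs and percentages move the same way, because boosted subjects enter them at the imputed 0.1 IU/mL. A sensitivity set with that property is a poor test of robustness.

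**Working it through.** The plan gives no sample size, power, drop rate or out-of-window rate on this point, so there is no figure to reproduce. The check is a row count followed by an illustration under stated assumptions.

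**1. Who the row can reach.**
- The 7-day draw exists only for subjects boosted in the study (SAP Section 3, Table 3 footnotes).
- In-study boosters go only to subjects with RVNA below 0.5 IU/mL (SAP Section 3), which is the event (Section 8.8).
- Subjects boosted in error at 0.5 IU/mL or above are already out at FAS-2 (Table 5).
- So within FAS-2 the row reaches only subjects with an event.

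**2. Whether the analyses use the draw.** The time-to-event analysis stops at the event. The long-term model uses annual Scheduled Clinic Visits (SAP Section 11.3), with values after the booster replaced. Neither uses the 7-day sample.

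**3. Row count in Table 5.**

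| Rows | Count |
|---|---|
| All rows | 34 |
| EXC for PPS-1 only (booster handling) | 8 |
| EXC for PPS-2 (34 − 8) | 26 |
| Of these, already EXC at FAS-2 | 7 |
| Rows that separate PPS-2 from FAS-2 (26 − 7) | 19 |
| Of these, specific to boosted subjects | 1 (the 7-day draw) |

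This rests on the column positions of the marks, which are consistent from row to row.

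**4. Size of the bias.** Let S be true persistence and q the share of boosted subjects out of window. If every event is followed by a booster and a 7-day draw, persistence in PPS-2 is S / (1 − (1 − S)q). Assume 40% drop in the accelerated arm and 20% in the conventional arms, with q = 10% in each:
- Accelerated: 0.60 / (1 − 0.40 × 0.10) = 0.60 / 0.96 = 62.5%.
- Conventional: 0.80 / (1 − 0.20 × 0.10) = 0.80 / 0.98 = 81.6%.
- Hazard ratio as the ratio of log persistence: ln 0.600 / ln 0.800 = 2.29 becomes ln 0.625 / ln 0.816 = 2.32.

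**5. Share of subjects removed.** The maxima in SAP Table 1 are 209 accelerated and 158 + 211 = 369 conventional, 578 in all. In the example the row removes (209 × 0.40 + 369 × 0.20) × 0.10 = 15.7 subjects, or 2.7% of 578. The range over other assumptions, with q equal across arms, is:

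| Assumed drop, accelerated / conventional | q | Persistence, accelerated | Persistence, conventional | Hazard ratio | Removed by this row |
|---|---|---|---|---|---|
| 20% / 10% | 5% | 80.0% to 80.8% | 90.0% to 90.5% | 2.12 to 2.12 | 3.9 (0.7%) |
| 40% / 20% | 10% | 60.0% to 62.5% | 80.0% to 81.6% | 2.29 to 2.32 | 15.7 (2.7%) |
| 60% / 30% | 20% | 40.0% to 45.5% | 70.0% to 74.5% | 2.57 to 2.67 | 47.2 (8.2%) |

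**6. Against the 10% trigger.** None of these scenarios reaches 10% through this row alone. In the middle one, if the other rows remove a share d of all subjects regardless of outcome, total exclusion is 0.027 + 0.973d. It passes 10% when d exceeds (0.10 − 0.027) / 0.973 = 7.5%. Removal unrelated to outcome leaves the 62.5% and 81.6% unchanged, so the bias comes from the 7-day row even when other rows bring PPS-2 into use.

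**The case against.** **Only part of the data may be excluded.** SAP Section 6.1 allows a major deviation to remove either the subject or some of the subject's data. If only the 7-day sample were dropped, persistence would be untouched. But Section 7.4 defines PPS-2 by subject, Table 5 carries one flag per set, and neither says that this row works by sample. Under that reading the mark would also be void for PPS-2, because the sample is not used there. Either way nothing is lost by deleting it.

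**PPS-2 is conditional and supportive.** This stands. The SAP states no null hypothesis, FAS-2 is unaffected, and the row alone does not reach 10% in the scenarios examined. The trigger counts all exclusions together, however. For example, an assumed, independent 2% chance per visit of an annual draw outside ±42 days, over seven windowed visits, gives 1 − 0.98^7 = 13% of subjects.

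**The figures are upper bounds.** This also stands. Subjects who first drop at Year 10 are boosted outside the study (Protocol Section 5.2), some miss the Ad hoc visit (Section 3.8), and some fail the criteria checked before the booster (Section 4.2). None of them has a 7-day draw.

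Three stronger inferences are tempting, and the documents do not support them:
- *PPS-2 removes events and nothing else.* This is true of the one row. The other 18 rows that separate PPS-2 from FAS-2 cover consent, eligibility, prohibited products, annual timing, sample handling and laboratory deviations, and subjects with or without an event can incur them. If those rows remove 2% to 5% of all subjects, then with 40%/20% drop and 5% to 10% out of window, events make up 42% to 69% of those removed.
- *PPS-2 could contradict FAS-2 solely because events were deleted.* In the scenarios examined PPS-2 is run only if other rows also exclude subjects, so a difference could not be put down to this row alone.
- *The annual-window row, "Did not comply with blood draw schedule (for annual Scheduled Clinic Visits): yearly blood draw outside +/- 42 days interval", should likewise be limited in PPS-1 to the visits on either side of the booster.* SAP Section 11.2 takes the preceding annual value as the GMR baseline, and Sections 8.5 and 11.4 use annual values after the booster for booster persistence. Such a limit would leave later annual draws in that analysis without a window rule.

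**Conclusion.** The point holds for this one row. As written, it can remove from PPS-2 only subjects with a persistence event, because of a sample that the persistence analyses ignore. It is out of line with the eight booster-handling rows in the same table. It also departs from the protocol's principle that booster correctness matters for boostability only, although the protocol's wording concerns receipt of the booster and not the timing of the draw.

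If PPS-2 is run, the bias is upward in each arm: at most 2.5 points (accelerated) and 1.6 points (conventional) in the middle scenario. The largest scenario examined gives 5.5 and 4.5 points. The hazard ratio is nearly unchanged provided the out-of-window share is the same across arms; the documents give no data on that. All drop and out-of-window rates here are assumptions. This is a worthwhile table correction to a conditional analysis set and does not threaten the main analysis on FAS-2.

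**What to change.** In SAP Table 5, delete EXC under PPS-2 for the code 2090 row on the 7-day post-booster draw and keep EXC under PPS-1. The row then matches the eight booster-handling rows, and none of the 18 remaining rows that separate PPS-2 from FAS-2 is specific to boosted subjects. Leave the annual-window row as it is. The cost is one table cell and the matching line in the PPS-2 flag program; no new data are needed and no subject with usable persistence data is lost.

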8. GENERAL ISSUES FOR STATISTICAL ANALYSES

8.1. Adjustment for Covariates

Cox proportional hazards regression model – Time to first RVNA <0.5IU/mL

The hazard ratio (HR) from the Cox ([Andersen](#), 1982) proportional hazards regression model will be used as a treatment effect measure for time to event endpoints.

Group comparisons for first occurrences of a booster (i.e., RVNA concentration <0.5 IU/mL) will be performed using an adjusted Cox proportional hazard regression model with effect for treatment and center. Ties will be handled with the exact method as it assumes that there is a true but unknown ordering for the tied event times.

Analysis of Variance (ANOVA) – Analysis of boostability.

For subjects who will receive rabies vaccine booster the log-transformed antibody concentration at day 7 will be analyzed using an Analysis of Variance (ANOVA) which includes treatment (vaccine received at time of parent study V49_23) and center. Summary tables will show adjusted GMCs and GMR for each treatment and adjusted ratios of GMCs between vaccine groups.

Mixed model for repeated measures – Analysis of persistence

Log-transformed antibody titers as collected at annual Scheduled Visits (from Visit 1 to Visit 7) will be analyzed using a mixed model for repeated measures within subject, including time and treatment as independent variables, their interaction and a random intercept with an unstructured covariance matrix.

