All sites will be trained in a uniform fashion and **those** sites will be monitored to ensure consistency in study execution across all centers.

Informed consent will be performed prior to any study-related procedures.

Subjects who sign the informed consent will be screened to assess for their eligibility of participation in the study.

All individuals who are screened for the study, as defined in this section, should be recorded on the “subject screening log” where information on the selection of potential participants in the trial should be collected. The reason why an individual was not enrolled, the enrollment date and assigned subject number and code which is carried over from the parent study, should be recorded by the investigator/study staff. It is the responsibility of the investigator/delegate to file this document among those of the Investigator Site File to be readily available for on-site monitoring and/or for inspection by the relevant authorities.

Subjects will receive their booster doses based on their own antibody concentrations (booster will be administered only to those subjects with RVNA concentrations <0.5 IU/mL), medical history and physical examination to ensure that they are in good health according to the investigator’s opinion and meet all inclusion criteria and none of the exclusion criteria.

For all subjects enrolled there will be overall 8 blood draws (of approximately 7 mL each) scheduled during the course of the extension study; each of these blood draws will be taken at each Scheduled Clinic Visit, from extension study Day 1 (Year 3 after completion of PrEP in the parent study V49_23) and then yearly through Year 10. During

Scheduled Clinic Visit and Additional Clinic Visit, subjects will be observed for at least 15 minutes after the blood draw for any adverse event (AE).

A urine pregnancy test will be performed for female subject of childbearing potential who are eligible to receive the booster dose prior to vaccination.

Vaccination procedures:

Only those subjects for which the RVNA concentration determined to be <0.5 IU/mL based on the blood sample from Visit 1, 2, 3, 4, 5, 6, and 7 (i.e., on Year 3, 4, 5, 6, 7, 8, and 9) will receive the booster dose of rabies vaccine in an open label fashion, time of each booster dose and blood draw for rabies antibody concentrations needs to be meticulously recorded.

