Additionally, all boosted subjects will be pooled together and their RVNA concentrations analyzed using an ANOVA model that includes vaccine regimen group and time in study of the booster dose as factors in the model along with their interaction. For this analysis, values, as measured at day 7 (and also approximately at 6 months) after booster dose, will be used.

Percentages of subjects with RVNA concentrations ≥ 0.5 IU/mL, as measured by RFFIT assay at 7 days after the booster dose and at subsequent scheduled clinical visit.

Percentages and 95% CIs will be presented by vaccine regimen.

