8.3. Multicenter Studies

Long-term persistence of antibody responses after primary series

Both time-to-event and persistence analyses will include term for center.

Boostability analysis

Geometric mean concentration analysis will be estimated using a two-way ANOVA including treatment and center.

If the statistical model does not converge due to the factor “center”, a model without center effect will be fitted instead.

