Estimation of survival functions

The term “survival function” $S(t)$ is used here in its general meaning as probability of experiencing a specific event at time t or later. The event of interest is the time when **RVNA concentrations < 0.5 IU/mL**.

A graphical estimate of the survival function separately for each vaccine schedule group will be obtained by the KM product - limit method as implemented in SAS PROC LIFETEST.

Together with the KM curve, the 95% CIs, will be estimated and displayed per each vaccination regimen. Standard errors of the KM estimates will be based on the Greenwood’s method; 25th and 75th percentile and median survival will be provided if estimable.

Data will include observations at 7 days after primary vaccine schedule and at 3, 5 and 12 months from the parent study (V49_23) and the year observations from this study.

```
PROC LIFETEST data=<dataset> plots=(survival(atrisk) logsurv);  
TIME survtime*Status(0);  
STRATA arm;  
RUN;
```

Immune response to booster dose

Geometric Mean Concentration and Geometric Mean Ratios (GMR)

For subjects receiving a booster dose, analysis of boostability will be conducted 7 days and 6 months after administration of the booster dose by providing GMRs and associated 95% CIs, considering the antibody value before the booster visit (i.e., 6 months before following the blood drawn during previous Scheduled Clinic Visit) as baseline (denominator) and the antibody concentration at 7 days and at 6 months after booster as the numerator.

Independently of the time (i.e., visit) a subject receives a booster dose of PCEC vaccine, RVNA concentration as detected from the blood drawn during previous scheduled clinic visit (approximately six months before the booster administration) will be considered baseline value and summarized by the mean of GMC, with associated 95% CIs, median, minimal and maximal values for each vaccine schedule group. In the same table the 7 days and 6 months post booster dose response and geometric mean ratio will be described. ***Percentage of subjects with RVNA concentrations ≥ 0.5 IU/mL***

No inferential model is defined for the binomial variable (i.e., subject with RVNA concentrations ≥ 0.5 IU/mL). Percentages of subjects at 7 days and at 6 months (i.e., at subsequent Scheduled Clinical Visit) after the booster dose will be presented together with 95% CIs (Clopper, 1934) by primary vaccine schedule (arm).

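### The SAP omits the protocol's booster-time analysis, so the day-7 GMC ratios between regimens combine regimen with time since priming, and no planned model shows the timing effect

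*SAP*

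**What the plan says.** SAP 8.1 (Adjustment for Covariates) states that "the log-transformed antibody concentration at day 7 will be analyzed using an Analysis of Variance (ANOVA) which includes treatment" and center, and promises adjusted GMCs and adjusted GMC ratios between vaccine groups. SAP 8.3 (Multicenter Studies) repeats the model: "Geometric mean concentration analysis will be estimated using a two-way ANOVA including treatment and center". Only day 7 is named in 8.1.

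Protocol 8.4.2.3.3 (Statistical Methods) first plans within-subject GMRs. It then adds: "Additionally, all boosted subjects will be pooled together and their RVNA concentrations analyzed using an ANOVA model". It describes this as an "ANOVA model that includes vaccine regimen group and time in study of the booster dose as factors in the model along with their interaction", to be run on the day-7 values and on those at about six months.

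The pre-booster value is collected. SAP 11.2 says "RVNA concentration as detected from the blood drawn during previous scheduled clinic visit (approximately six months before the booster administration) will be considered baseline" and uses it as the GMR denominator. It is a covariate in neither the SAP model nor the protocol model.

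**The concern.** The time of a booster is set by the subject's own antibody decline. SAP 11.2 records that the accelerated and conventional schedules had already separated in persistence by Day 366 of the parent study, so the arms can be expected to reach the booster at different times since priming. A between-regimen ratio adjusted for center alone then mixes two things: what the primary schedule did to the capacity to respond, and how long after priming the booster was given.

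The second is a study question in its own right. Protocol 1.1 says the study will characterize the need for and timing of a booster after the accelerated regimen. Protocol 8.6 foresees submitting the interim report if the results support a booster at a given time after priming. The analysis left out of the SAP is the only planned model that relates booster response to that time.

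**Working it through.** **1. The texts side by side.** The documents give no sample size, SD or correlation for the booster analysis, so there is no figure to reproduce.

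| Term | SAP 8.1 / 8.3 | Protocol 8.4.2.3.3, additional ANOVA |
|---|---|---|
| Regimen | yes | yes |
| Center | yes | no |
| Booster time | no | yes |
| Regimen × booster time | no | yes |
| Pre-booster RVNA | no | no |
| Time points | day 7 | day 7 and about six months |

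Two other SAP sections come close but do not fill the gap. SAP 8.5 groups FAS-1 by year of booster, descriptively and only for persistence after the booster. SAP 11.4 models annual values after the booster, where time means time since the booster. The history of changes mentions neither the removal of the protocol model nor a reason for it.

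**2. Why timing can differ by arm.** In the study, "booster will be administered only to those subjects with RVNA concentrations <0.5 IU/mL". Subjects found below the cut-off at a Scheduled Visit ("i.e., on Year 3, 4, 5, 6, 7, 8, and 9) will receive the booster dose of rabies vaccine") can be boosted at any of seven times. All enter about three years after priming, so booster time in the study and time since priming differ by roughly a constant.

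**3. How far timing could move the ratio (inputs assumed).** Shift in log10 GMC ratio = yearly slope × difference in mean booster year. Take a slope of ±0.05 log10 per year (10^0.05 = 1.12, about 12% per year) and mean booster years of 4.41 and 6.0, a gap of 1.59.
- 0.05 × 1.59 = 0.08 log10, so the ratio moves to 10^−0.08 = 0.83 or 10^0.08 = 1.20.
- With a slope of zero the shift is zero.

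A simulation of the accelerated against the Conv-R arm agrees. It used 1,500 runs, no true regimen effect, SD 0.5 log10 and no center term. The regimen-only contrast shifted by 0.079 to 0.085 log10 in size. With booster year in the model it stayed within 0.006 of zero.

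**4. What pre-booster RVNA would add.** CI width ratio = √(1 − ρ²). Values before in-study boosters are cut off below 0.5 IU/mL and, going by SAP 8.8, recorded at five levels ("IF LBORRES IN ('<0.1', '0.1', '0.2', '0.3', '0.4"). Simulating that cut-off and rounding lowers assumed correlations of 0.3, 0.5 and 0.7 to about 0.13–0.15, 0.22–0.25 and 0.36–0.40.
- ρ = 0.13: √(1 − 0.017) = 0.99, about 1% narrower.
- ρ = 0.40: √(1 − 0.16) = 0.917, about 8% narrower.

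**5. What booster year costs.** Same simulation, zero slope, correlation 0.3. Boosted counts are assumed, in the order Conv-R/JE, Acc-R/JE, Conv-R.

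| Model | SE, 70 boosted (10/45/15) | SE, 130 boosted (20/80/30) |
|---|---|---|
| Regimen | 0.152 | 0.107 |
| + pre-booster RVNA | 0.145 | 0.103 |
| + booster year | 0.170 | 0.117 |
| + both | 0.164 | 0.112 |

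Booster year widens the interval (0.170/0.152 = 1.12; 0.117/0.107 = 1.09), and the covariate recovers only part of that. The full interaction has 3 × 7 = 21 cells. All were filled in about 3% of runs with 70 boosted and in 61–64% with 130.

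**The case against.** The strongest case is that little rests on this ratio. Primary objective 2 is to evaluate the booster response, not to compare regimens. Its endpoints are GMCs, within-subject GMRs and the percentage at or above 0.5 IU/mL. There is no hypothesis and no success criterion, and the protocol itself labels the booster-time model as additional. The GMR already uses the pre-booster value. The protocol analysis was never formally withdrawn, and the interaction may not be estimable.

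Most of that stands and limits the weight of the point. It does not remove it. The SAP plans to report between-regimen ratios, and a protocol analysis that the SAP neither carries nor retires may simply not be programmed. Sparse cells are a reason for grouping years or dropping the interaction, not for leaving out booster time without comment.

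A reader might go further and infer that the regimen comparison is confounded by time since priming and that the unadjusted ratio is biased by a known factor. The documents do not support that. Regimen was randomized in the parent study, and booster time and pre-booster RVNA are consequences of it, seen in subjects selected because their RVNA fell. Conditioning on them answers a different question and does not restore a randomized comparison. A reader might also infer that the SAP model is materially less precise. Only pre-booster RVNA bears on that, and modestly; booster year works the other way.

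**Conclusion.** The point holds as an unexplained departure of the SAP from the protocol, with a consequence for interpretation. The day-7 GMC ratios between regimens combine regimen with booster timing, and no planned model describes how booster response varies with time since priming.

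The size cannot be read from the documents. A 1.6-year gap and 12% per year would put the ratio at about 0.83 or 1.20 through timing alone; a flat response would leave it untouched, and the omitted analysis is what would tell these apart. The gain from pre-booster RVNA is about 1–8% of CI width. Slope, gap, SD, correlations and boosted counts are all assumptions. The change should be made, but the within-subject GMRs and the percentages at or above 0.5 IU/mL do not depend on it.

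**What to change.** Keep the regimen-plus-center GMCs and the GMRs as planned. In SAP 8.1 and 8.3, restore the protocol's booster-time analysis beside them, for day 7 and about six months:
- log10 RVNA on regimen and booster year, with year continuous or grouped. Fit the main effect first, and the interaction only where the cells allow, with the grouping rule written down beforehand.
- log10 pre-booster RVNA from the last Scheduled Visit as a covariate, for subjects boosted in the study.
- Subjects boosted before entry, whom SAP 7.3 admits to FAS-1 regardless of RVNA, left out of this model. For that booster they have no comparable baseline and no study day-7 sample.
- A sentence stating that the booster-time-adjusted regimen ratio is a conditional, descriptive contrast and not a correction of confounding.

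If the sponsor prefers not to run the analysis, the SAP should say so and give the reason. The cost is a few lines of SAS and SAP wording, with no new data. The downside to note is that adding booster year may widen the interval for the adjusted ratio: 9–12% in the examples above, less once pre-booster RVNA is included.
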